### 4.3 Definition of end of study

Timing of the randomized and non-randomized primary analysis is directly driven by the enrollment of the expansion arm of each section, and the primary analysis of each section will be run once the expanded arm has fully enrolled and also after all patients randomized/enrolled in that arm had at least 9 months of follow-up. This timing would allow for a potential minimum duration of response of 6 months for all subjects randomized/enrolled, assuming no delayed response. The exact timing of the randomized primary analysis could be revisited if more than one arm ends up being expanded.

Following the cut-off date for the primary analysis, the study will remain open. Ongoing subjects will continue to receive study treatment and will be followed as per the schedule of assessments, as long as subjects derive benefit from the combination arms in the opinion of the investigator.

The end of study is defined as the earliest occurrence of one of the following:

- All subjects have died or discontinued from the study
- Another clinical study (i.e. rollover study) becomes available that can continue to provide the appropriate combination treatment in this subject population and all subjects ongoing are eligible to be transferred to that clinical study
- All subjects randomized/enrolled in the study have at least 15 months of follow-up (i.e. 15 months after last subject is randomized/enrolled). For subjects still receiving study treatment at the time of end of study, every effort will be made to continue provision of study treatment outside this study through an alternative setting (e.g. Novartis managed access program) to subjects who in the opinion of the investigator are still deriving clinical benefit.

The final analysis and the generation of the final CSR will occur at the end of the study.

The timing of primary and final analyses and the definition of end of study will be updated, should new arms be added through protocol amendment or if more than one arm is expanded to part 2.

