### **Safety follow-up**

[figure not shown]
After study treatment discontinuation, all subjects must be followed for safety evaluations up to 150 days after the last dose of study treatment as outlined in [Section 7.1.7](#).

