### 6.3.1.3.2 Dose modification for potential immune-mediated adverse events (irAEs)

Adverse events of special interest include irAEs that are associated with spartalizumab/LAG525 treatment. An irAE may be experienced by subjects treated with spartalizumab or/and LAG525 due to their mechanism of action and predicted based on the reported experience with other checkpoint inhibitors that have a similar mechanism of action. Investigators must be vigilant and carefully identify AEs that may be suggestive of potential irAEs as their appearance may be sub-clinical and early diagnosis is critical for adequate management and resolution.

Immune-related adverse events may be of low grade and self-limited, most frequently involving the gastrointestinal tract (e.g. diarrhea/colitis), skin (e.g. rashes, pruritus), liver (e.g. hepatitis), lung (e.g. pneumonitis), kidneys (e.g. nephritis) and endocrine systems (e.g. hypothyroidism, hyperthyroidism, type I diabetes, hypophysitis including hypopituitarism and adrenal insufficiency). Other immune-related AEs may rarely include the nervous system (e.g. encephalitis, Guillain-Barre syndrome, myasthenia gravis), eye (e.g. uveitis, vision changes), musculo-skeletal system (e.g. myositis, arthritis), pancreas (e.g. pancreatitis), cardio-vascular system (e.g. vasculitis, myocarditis) or blood system (e.g. anemia, cytopenias), and severe skin reactions such as toxic epidermal necrolysis or Stevens-Johnson syndrome. Furthermore, complications in patients with bone marrow or solid organ transplant have been reported (e.g. organ rejection, severe graft-versus-host disease). However, nearly all organs can be affected by immune-mediated toxicities. IrAEs often occur relatively early (mostly within weeks to 3 months after treatment initiation), however, may develop at any time during treatment (even after several months), and may also occur after treatment discontinuation. Serological, immunological and histological assessments should be performed as deemed appropriate by the investigator, to verify the potential immune-mediated nature of the AE, and exclude neoplastic, infectious or metabolic origin of the AE.

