### 6.3.3 Follow-up for toxicities

All subjects must be followed-up for AEs and SAEs for 150 days following the last dose of spartalizumab/LAG525, or up to 130 days after the last dose of canakinumab, or up to 30 days after the last dose of capmatinib or ribociclib, whichever is later. Suspected SAEs will continue to be collected beyond those timeframes. However, if the subject begins subsequent anti-cancer therapy before the 150-Day safety visit, the collection of new SAEs and AEs unrelated to study medication will stop and thereafter only suspected SAEs and suspected AEs will continue to be collected up to 150 days following the last dose of spartalizumab. If SAEs suspected to be related to study medication occur beyond Day 150, information should also be collected.

The emergence of irAEs may be anticipated based on the mechanism of action of checkpoint inhibitor therapies. Serologic, histologic (tumor sample) and immunological assessments should be performed as deemed appropriate by the Investigator to verify the immune-related nature of the AE and to exclude alternative explanations. Recommendations have been developed to assist investigators in assessing and managing the most frequently occurring irAEs (refer to [Appendix 3](#)). If cytokine release syndrome is suspected, the assessments outlined in [Section 7.2.2.5](#) must be performed.

Subjects whose treatment is interrupted or permanently discontinued due to an irAE, AE or clinically significant laboratory value, must be followed-up at least once a week (or more frequently if required by institutional practices, or if clinically indicated) for 30 days, and subsequently at approximately 30-day intervals (or more frequently if required by institutional practices, or if clinically indicated), until resolution or stabilization of the event, whichever comes first. Appropriate clinical experts should be consulted as deemed necessary.

Refer to [Section 6.3](#) and [Appendix 3](#) for the follow-up evaluations recommended for selected toxicities.

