	Category	Protocol section	Screening period	Treatment Period (Cycle = 28 days)							Follow-up (FU) Period						Survival			
			Screening	Cycle 1			Cycle 2		Cycle 3		Subsequent Cycles Day 1	End of Treatment (EoT)	Safety FU					Efficacy FU (Not applicable if EoT due to progression)		
				1	8	15	21	1	1	8			15	1	30-day Safety FU	60-day Safety FU			90-day Safety FU	120-day Safety FU
Day of cycle			-28 (-35 for arm 1A) to -1	1	8	15	21	1	1	8	15	1								
CT/MRI of other metastatic sites (e.g. neck)	D	7.2.1	If clinically indicated or if lesions were documented at screening, follow same schedule as CT/MRI of chest, abdomen, and pelvis.																	
Localized bone CT, MRI or X-ray	D	7.2.1	Only for lesions on whole body scan that are not visible on the chest, abdomen and pelvis scans. If lesions were documented at screening, follow same schedule as CT/MRI of chest, abdomen and pelvis																	
Color Digital Photography (including a metric ruler)	D	7.2.1	X	If clinically indicated or if cutaneous lesions were documented at screening, follow same schedule as CT/MRI of chest, abdomen, and pelvis.																
Collection of body fluid/tissue data	D	7.2.1	Record needle aspiration, biopsy or any other form of collection (e.g., paracentesis, puncture) performed for any clinically indicated reason																	
Safety																				
Adverse events (AEs)	D	8.1.1	Suspected AEs up to 150 days after last spartalizumab dose regardless of the start of subsequent anti-cancer therapy; non-suspected AEs up to 150 days after last spartalizumab dose or start of subsequent anti-cancer therapy, whichever is sooner.																	
Serious adverse events (SAEs)	D	8.1.2	Suspected SAEs up to 150 days after last spartalizumab dose and beyond, regardless of the start of subsequent anti-cancer therapy; non-suspected SAEs up to up to 150 days after last spartalizumab dose or start of subsequent anti-cancer therapy, whichever is sooner.																	

[figure not shown]
	Category	Protocol section	Screening period	Treatment Period (Cycle = 28 days)										Follow-up (FU) Period						Survival		
			Screening	Cycle 1			Cycle 2			Cycle 3			Subsequent Cycles Day 1	End of Treatment (EoT)	Safety FU						Efficacy FU (Not applicable if EoT due to progression)	
				1	8	15	21	1	8	15	1	30-day Safety FU			60-day Safety FU	90-day Safety FU	120-day Safety FU	150-day Safety FU				
Day of cycle			-28 (-35 for arm 1A) to -1	1	8	15	21	1	8	15	1											

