### **10.5.3 Safety objectives**

#### **10.5.3.1 Analysis set and grouping for the analyses**

For all safety analyses, the safety set will be used. All listings and tables will be presented by treatment group. In addition, pooled safety analysis based on all subjects will be produced.

The overall observation period will be divided into three mutually exclusive segments:

1. pre-treatment period: from day of subject's informed consent to the day before first dose of study medication
2. on-treatment period: from day of first dose of study medication to 30 days after last dose of study medication
3. post-treatment period: starting at day 31 after last dose of study medication.

If dates are incomplete in a way that clear assignment to pre-, on-, or post-treatment period cannot be made, then the respective data will be assigned to the on-treatment period. Additional details to address incomplete AE and/or dosing dates will be addressed in the SAP.

Additional summaries will be displayed to report deaths, all AE, AE related to study treatment, all SAE and SAE related to study treatment collected up to 150 days after last administration of spartalizumab.

Safety will be assessed based on all treated subjects; toxicities will be defined by CTCAE v5. Incidence and severity of adverse events, causality attribution to drug, time to event onset, duration of the event, its resolution and concomitant medications administered will be recorded. Additional safety assessments will include laboratory safety assessment, vital signs, and cardiac assessment.

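### The 15-month end-of-study trigger can close the trial before the mandated 150-day safety follow-up is complete, and the adverse-event window in Table 7-2 conflicts with the text

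*Protocol*

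**What the plan says.** **End of study.** Protocol section 4.3 states: "The end of study is defined as the earliest occurrence of one of the following". The three events are that all subjects have died or left the study, that a rollover study becomes available to which ongoing subjects can transfer, and "All subjects randomized/enrolled in the study have at least 15 months of follow-up (i.e. 15 months after last subject is randomized/enrolled". The only provision made at that point is for people on drug: "For subjects still receiving study treatment at the time of end of study, every effort will be made to continue provision of study treatment" outside the study.

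**Safety follow-up.** Under its safety follow-up heading, section 4.1.3 says that "all subjects must be followed for safety evaluations up to 150 days after the last dose of study treatment". Section 7.1.7 repeats the requirement and gives the antibodies' long half-life and checkpoint-inhibitor side effects as the reason.

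**Adverse-event window in the text.** Besides 150 days after spartalizumab/LAG525, section 6.3.3 gives "or up to 130 days after the last dose of canakinumab, or up to 30 days after the last dose of capmatinib or ribociclib, whichever" comes later. Sections 7.1.7, 8.1.1 and 8.1.2.2 apply the same principle using the longest window. Section 6.3.1 allows one drug of a pair to be stopped alone, except in arm 1.

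**Adverse-event window in the schedule and analysis.** The adverse-event row of Table 7-2 reads "Suspected AEs up to 150 days after last spartalizumab dose regardless of the start of subsequent anti-cancer therapy". Non-suspected adverse events and non-suspected serious adverse events have the same limit, or the start of new therapy if sooner. The additional summaries in section 10.5.3.1 cover deaths, adverse events and "all SAE and SAE related to study treatment collected up to 150 days after last administration of spartalizumab".

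**The concern.** Treatment has no fixed maximum duration (section 6.1.5), so last doses can fall at any time up to closure. A subject who stopped shortly before the 15-month date is no longer on treatment, so the supply provision in 4.3 does not apply. That subject is still inside the mandated safety window, and 4.3 makes no provision for completing it. The rollover trigger carries no such condition either.

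The subjects affected tend to be those treated longest. Section 6.3.1.3.2 says that immune-related events "may develop at any time during treatment (even after several months), and may also occur after treatment discontinuation", and the 150-day window exists to capture such late events. The day-150 visit also includes the final serum pregnancy test, which matches the 150-day contraception requirement in exclusion criterion 15a.

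The second issue is smaller. Where spartalizumab is stopped and the partner drug continues, a site working from Table 7-2 would end routine adverse-event collection earlier than sections 6.3.3, 7.1.7, 8.1.1 and 8.1.2.2 require.

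**Working it through.** The plan gives no figure of its own to reproduce. The check is date arithmetic, plus an illustration under stated assumptions.

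**(a) End of study against safety follow-up**

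Inputs: 15 months (4.3); 150 days (4.1.3, 7.1.7); 28-day cycles (6.1.1). I take 30.44 days per month and count the first dose as day 1 at enrolment.

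- Trigger date for the last-enrolled subject: 15 × 30.44 = 456.6, about day 457.
- Latest last dose that still allows 150 days: 456.6 − 150 = 306.6, about day 307 (10.1 months).

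| Last dose at | Day | Day + 150 | Result |
|---|---|---|---|
| C11D1 | 281 | 431 | complete |
| C12D1 | 309 | 459 | about 2 days short |
| C13D1 | 337 | 487 | about 30 days short |
| C15D1 | 393 | 543 | about 86 days short |
| C17D1 | 449 | 599 | about 142 days short |

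No passage resolves this. Section 4.1.3 lists end of study among the events that stop survival follow-up, and sponsor termination among those that stop efficacy follow-up. Neither appears in the safety follow-up text. Section 4.4 asks for subjects to be seen, but covers early termination only.

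The share of subjects affected depends on time on treatment, which the protocol does not give. Assume exponential time on treatment with median m months, and follow-up f at closure uniform on 15 to 27 months (12-month uniform accrual). With w = 150/30.44 = 4.93 months:

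P(last dose within the final w months) = 2^(−(f−w)/m) − 2^(−f/m)

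| Median m | Averaged over f = 15 to 27 | Last-enrolled subject, f = 15 |
|---|---|---|
| 3 months | 0.022 | 0.066 |
| 6 months | 0.073 | 0.136 |
| 9 months | 0.095 | 0.145 |

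For arm 1A at its maximum of about 100 subjects, this is about 2, 7 or 10 people. On the same assumptions a further 1%, 10% or 21% are still on treatment at closure, which matters for how the fix is worded.

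**(b) Table 7-2 against the text**

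Let the partner drug's last dose fall k days after the last spartalizumab dose. The window required by 6.3.3, counted from the last spartalizumab dose, is:

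- canakinumab: max(150, k + 130), so the table falls short by max(0, k − 20);
- capmatinib or ribociclib: max(150, k + 30), so the table falls short by max(0, k − 120).

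For canakinumab, k = 28, 56 and 168 give shortfalls of 8, 36 and 148 days. For the oral drugs, k = 150 and 168 give 30 and 48 days. Beyond k = 150 the table's limit passes while study drug is still being taken.

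Two limits apply. The serious-adverse-event row continues suspected serious events past day 150. And section 10.5.3.1 defines the on-treatment period as running to 30 days after the last study medication, not the last spartalizumab dose, so the main tables in 10.5.3.2 are not cut at the spartalizumab limit.

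**The case against.** **On (b).** A reader might infer that Table 7-2 stops all adverse-event and serious-adverse-event collection, and that events on a continuing partner drug are neither collected nor counted. The documents do not support this. Suspected serious events continue without limit in the same table. The rows cite sections 8.1.1 and 8.1.2, which contain the longer rule. Section 7.1 keeps visits and safety assessments going when one drug stops, and section 7.2.2 has adverse events collected at every visit. The main on-treatment tables would include such events, and 10.5.3.2 lists all adverse events, post-treatment ones included. This objection stands: (b) is a wording conflict about adverse events and non-suspected serious events, plus one set of additional summaries with a narrower limit. Its reach is also small. Arm 1 must stop both drugs together, arm 1A's partner LAG525 has its own 150-day window, and arms 2 to 4 have all been declared futile.

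**On (a).** The medians and the accrual period are invented. At the second interim analysis of arm 1, section 2.4.1.1 reports a response rate of 8.6% and discontinuation for progression in 57.1%, which gives no support for a 9-month median. Some subjects counted as affected would lose only days. In the rollover trigger, the term for ongoing subjects is undefined and could be read to include those in safety follow-up. These points limit the size. They do not remove the conflict, because no passage makes closure wait for the safety window.

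**Conclusion.** Part (a) holds. Section 4.3 can end the study while subjects are still inside the safety follow-up that 4.1.3 and 7.1.7 require of everyone. The day-307 limit for the last-enrolled subject follows from the protocol's own figures and the month conversion. The 2%, 7% and 10% rest wholly on the assumed exponential times on treatment and 12-month accrual, and should be read as a range, with its upper end depending on a median that nothing in the protocol supports. It applies to every arm, including arm 1A.

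Part (b) holds as a narrower inconsistency: Table 7-2 and the additional summaries in 10.5.3.1 use a spartalizumab-only limit that disagrees with four text sections, for adverse events and non-suspected serious adverse events in the table. It concerns only subjects remaining in arms 2 to 4 who continue the partner drug alone. The protocol does not say how many there are.

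**What to change.** Reconcile section 4.3 with 4.1.3 and 7.1.7. One way is to make the 15-month and rollover triggers conditional on completion of the section 7.1.7 safety follow-up by subjects who have already stopped treatment at the trigger date, or who have died, withdrawn or been lost. The restriction to that date is needed: if closure waited for everyone who stops later, each new discontinuation would restart the clock and the delay would have no bound. With the restriction, close-out moves by at most about 150 days. The 60-, 90- and 120-day contacts may be by telephone, with clinic visits at days 30 and 150.

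Reconcile the adverse-event and serious-adverse-event rows of Table 7-2, and the additional summaries in 10.5.3.1, with sections 6.3.3, 7.1.7, 8.1.1 and 8.1.2.2, so that one collection window is stated throughout. This costs wording only.

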## 4.4 Early study termination

The study can be terminated at any time for any reason by Novartis. Should this be necessary, the subject should be seen as soon as possible and the same assessments should be performed as described in [Section 7](#) for a discontinued or withdrawn subject. The investigator may be informed of additional procedures to be followed in order to ensure that adequate consideration is given to the protection of the subject's interests. The investigator will be responsible for informing IRBs and/or ECs of the early termination of the trial.

## 5 Population

### 5.1 Patient population

The investigator or designee must ensure that only subjects who meet all the following inclusion and none of the exclusion criteria are offered treatment in the study.

### 5.2 Inclusion criteria

#### 5.2.1 Inclusion criteria for arms 1, 2, 3, 4

Subjects eligible for inclusion in this study have to meet **all** of the following criteria:

1. Written informed consent must be obtained prior to any screening procedures.
2. Male or female must be  $\geq 18$  years of age at time of providing informed consent.
3. Histologically confirmed unresectable or metastatic stage IIIB/C/D or IV melanoma using AJCC Edition 8 (refer to [Appendix 1](#))
- 4a. Previously treated for unresectable or metastatic melanoma:
  - Subjects with V600*BRAF* wild-type disease:
    - Subjects must have received prior systemic therapy for unresectable or metastatic melanoma with anti-PD-1/PD-L1. Additionally, subjects may have received anti-CTLA-4 as a single agent or in combination with anti-PD-1/PD-L1, irrespective of the sequence. No additional systemic treatment is allowed for advanced or metastatic melanoma
    - A maximum of two prior lines of systemic therapies for unresectable or metastatic melanoma are allowed.
    - The last dose of prior therapy (anti-PD-1, anti-PD-L1 or anti-CTLA-4) must have been received more than four weeks before randomization.
  - Subjects with V600*BRAF* mutant disease:
    - Subjects must have received prior systemic therapy for unresectable or metastatic melanoma with anti-PD-1/PD-L1, and V600*BRAF* inhibitor. Additionally, subjects may have received anti-CTLA-4 as a single agent or in combination with anti-PD-1/PD-L1, or MEK inhibitor (in combination with V600*BRAF* inhibitor or as a single agent), irrespective of the sequence. No additional systemic treatment is allowed for advanced or metastatic melanoma
    - A maximum of three prior lines of systemic therapies for unresectable or metastatic melanoma are allowed

- The last dose of prior therapy must have been received more than 4 weeks (for anti-PD-1, anti-PD-L1 or anti-CTLA-4) or more than 2 weeks (for V600*BRAF* or MEK inhibitor) prior to randomization
  - For all subjects with V600*BRAF* wild-type disease and with V600*BRAF* mutant disease: Subject must have documented disease progression as per RECIST v1.1 while on/after the last therapy received prior to study entry and while on/after treatment with anti-PD1/PD-L1. The last progression must have occurred within 12 weeks prior to randomization in the study
5. ECOG performance status 0-2
  6. At least one measurable lesion per RECIST v1.1 (refer to [Appendix 2](#))
  - 7a. At least one lesion, suitable for sequential mandatory tumor biopsies (screening and on-treatment) in accordance with the biopsy guidelines specified in protocol [Section 7.2.3.1.1](#). The same lesion must be biopsied sequentially. Note: this lesion cannot be used as a target lesion.
  - 8a. Screening tumor biopsy must fulfill the tissue quality criteria outlined in [Section 7.2.3.1.1](#), as assessed by a local pathologist
  - 9a. Subject must meet the following laboratory values at the screening visit in the absence of growth factors and/or transfusion support within 14 days prior to screening blood draw:

**Hematological**

- Hemoglobin  $\geq 9$  g/dL
- Absolute neutrophil count  $\geq 1.5 \times 10^9/L$
- Platelets  $\geq 75 \times 10^9/L$

**Renal**

- Serum creatinine  $< 1.5$  mg/dL

